6.6 Dose Modification

Lenvatinib dose reduction and interruption for participants who experience lenvatinib-related toxicity will be in accordance with the dose modifications described in [Table 3](#). AEs will be graded using CTCAE v5.0.

Asymptomatic laboratory abnormalities, including Grade ≥ 3 abnormalities (eg, elevations of amylase and lipase) that are not considered clinically relevant by the investigator should be managed per institutional guidelines; continuation of treatment should be discussed with the Sponsor.

Dose reductions will occur in succession based on the previous dose. Each reduction is a 20% reduction from the previous dose. Once the dose has been reduced, it cannot be increased at a later date, unless the dose has been mistakenly decreased; in this situation, Sponsor's approval is required to increase the dose. An interruption of lenvatinib >28 days will require consultation between the investigator and the Sponsor and written documentation of the collaborative decision on participant management.

Table 3 Criteria for Temporary Discontinuation of Study Drug, Dose Reduction, and Resumption of Treatment

Dose Modification Guidelines for Lenvatinib-Related Toxicity		
Treatment-Related Toxicity^{a,b}	Management	Dose Adjustment
Grade 1 or Tolerable Grade 2		
	Continue treatment	No change
Intolerable Grade 2^{c, d} or Grade 3^e		
First occurrence	Interrupt lenvatinib until resolved to Grade 0-1 or tolerable Grade 2	11.2 mg/m ² (or 20% reduction of the starting dose) orally QD (1-level reduction)
Second occurrence (same toxicity or new toxicity)	Interrupt lenvatinib until resolved to Grade 0-1 or tolerable Grade 2	9.0 mg/m ² (or 20% reduction of the previous dose) orally QD (1-level reduction)
Third occurrence (same toxicity or new toxicity)	Interrupt lenvatinib until resolved to Grade 0-1 or tolerable Grade 2	7.2 mg/m ² (or 20% reduction of the previous dose) orally QD (1-level reduction)
Fourth occurrence (same toxicity or new toxicity)	Interrupt lenvatinib	Discuss with Sponsor
Grade 4^f: Discontinue Study Treatment		
Abbreviations: BMI = body mass index; CTC = Common Toxicity Criteria; CTCAE = Common Terminology Criteria for Adverse Events; QD = once daily. Note: For grading, see CTCAE version 5.0. Collect all CTC grades of adverse events, decreasing and increasing grade.		

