6.6.3 Management of Proteinuria

Regular assessment for proteinuria should be conducted as detailed in the SoA (Table 1). Guidelines for assessment and management of proteinuria are summarized as follows:

Grading of Proteinuria

- Grading according to CTCAE v5.0 will be based on the protein-creatinine ratio or 24-hour urinary protein result if available. For participants ≥18 years of age, if the participant has 4+ proteinuria by dipstick (≥1000 mg/dL by urinalysis), a 24-hour urinary protein result is required to confirm Grade 3 proteinuria.

Management of Proteinuria

- Management of lenvatinib administration will be based on the grade of proteinuria according to Table 3.

- In the event of nephrotic syndrome, lenvatinib must be discontinued.

Detection and Confirmation

- Perform urine dipstick testing per the SoA (Table 1). Urine dipstick testing is the preferred method for testing for urinary protein, however, urinalysis may be used if the use of urine dipsticks is not feasible.
- For participants ≥ 18 years of age, a 24-hour urine collection (initiated as soon as possible and at least within 72 hours) or an immediate spot P/C test AND for participants < 18 years of age, an immediate spot P/C test, and if possible, a 24-hour urine collection (initiated as soon as possible and at least within 72 hours) is required in the following situations:
 - The first (initial) occurrence of $\geq 2+$ (≥ 100 mg/dL) proteinuria on urine dipstick (or urinalysis) while on lenvatinib.
 - A subsequent increase in severity of urine dipstick or urinalysis proteinuria occurring on the same lenvatinib dose level.
 - When there has been a lenvatinib dose reduction and at the new dose level the urine protein dipstick result is $\geq 2+$ (≥ 100 mg/dL).

Note: For participants ≥ 18 years of age, a 24-hour urine collection (initiated as soon as possible and at least within 72 hours) to verify the grade of proteinuria is required when P/C test is ≥ 2.4 .

Monitoring

- Urine dipstick or urinalysis testing for participants with proteinuria $\geq 2+$ (≥ 100 mg/dL) should be performed on Day 15 (or more frequently as clinically indicated) until the results have been 1+(10 mg/dL) or negative for 2 consecutive 28-day treatment cycles.
- Proteinuria monitoring can be performed at the local laboratory or investigator site but must be managed by the site physician.

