Key Secondary Endpoints	
 • ORR • BOR • DOR • DCR • CBR • PFS per RECIST 1.1 or RANO for HGG • AEs, SAEs, clinical laboratory values, vital signs, 12-lead ECGs, urine dipstick, Lansky play scores or Karnofsky performance status scores, physical examination findings, dental examination findings, height, and closure of proximal tibial plates. • Palatability questionnaire using a facial hedonic scale.

Statistical Methods for Key Efficacy Analyses	To evaluate for efficacy of lenvatinib, data on antitumor activity will be analyzed by each tumor type. Objective responses will count only confirmed CR and PR at Week 16. Estimated ORR and its exact 95% CI using the method of Clopper and Pearson will be presented. The ORR, DCR, and CBR will be provided with exact 95% CIs using the method of Clopper and Pearson, and the DOR will be analyzed for responders using Kaplan-Meier approach. PFS will be analyzed using Kaplan-Meier product-limit estimates. The cumulative PFS probabilities will be plotted over time as appropriate.
Statistical Methods for Key Safety Analyses	The incidence of treatment-emergent adverse events (TEAEs) and SAEs will be summarized by system organ class and preferred term. Continuous measures such as changes from baseline in laboratory test data, vital signs, 12-lead ECGs, cardiac function by echocardiography or MUGA scan, urine dipstick, and Lansky play scores or KPS scores will be summarized using descriptive statistics (mean, standard deviation, etc.) for baseline, on-treatment, and change-from-baseline values.
Interim Analyses	Multiple interim analyses may be performed in this study due to the sequential monitoring procedure. Results will be reviewed by the study team. Within each tumor type, the study will enroll a minimum of 9 evaluable participants.
Multiplicity	No additional multiplicity adjustment is required for this study.
Sample Size and Power	CCI

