9.6.2 Statistical Methods for Safety Analyses

Safety and tolerability will be assessed by clinical review of all relevant parameters, including AEs, laboratory tests, and vital signs. Safety summaries will be pooled across all indications. The additional safety analyses for each tumor type might be conducted if desired and will be documented in the sSAP. The safety analysis population will be used for the analysis of safety data. TEAE is defined as all AEs from the treatment start date until 30 days after last dose (30 days for SAE). The incidence of TEAEs and SAEs will be summarized by system organ class and preferred term. Continuous measures such as changes from baseline in laboratory test data, vital signs, 12-lead ECGs, cardiac function by echocardiography or MUGA scan, urine dipstick, and Lansky play scores or KPS scores will be summarized using descriptive statistics (mean, standard deviation, etc.) for baseline, on-treatment, and change-from-baseline values.

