10.3.2 Definition of AE

AE definition

- An AE is any untoward medical occurrence in a clinical study participant, temporally associated with the use of study intervention, whether or not considered related to the study intervention.
- NOTE: An AE can therefore be any unfavorable and unintended sign (including an abnormal laboratory finding), symptom, or disease (new or exacerbated) temporally associated with the use of a study intervention.
- NOTE: For purposes of AE definition, study intervention (also referred to as Sponsor's product) includes any pharmaceutical product, biological product, vaccine, diagnostic agent, or protocol specified procedure whether investigational or marketed (including placebo, active comparator product, or run-in intervention), manufactured by, licensed by, provided by, or distributed by the Sponsor for human use in this study.

Events meeting the AE definition

- Any abnormal laboratory test results (hematology, clinical chemistry, or urinalysis) or other safety assessments (eg, ECG, radiological scans, vital signs measurements), including those that worsen from baseline, considered clinically significant in the medical and scientific judgment of the investigator.
- Exacerbation of a chronic or intermittent pre-existing condition including either an increase in frequency and/or intensity of the condition.

- New conditions detected or diagnosed after study intervention administration even though it may have been present before the start of the study.
- Signs, symptoms, or the clinical sequelae of a suspected drug-drug interaction.
- Signs, symptoms, or the clinical sequelae of a suspected overdose of either study intervention or a concomitant medication.
- For all reports of overdose (whether accidental or intentional) with an associated AE, the AE term should reflect the clinical symptoms or abnormal test result. Lenvatinib overdose without an associated adverse event is not reportable as an AE. Refer to Section 8.5 for the definition of overdose.

Events NOT meeting the AE definition

- Medical or surgical procedure (eg, endoscopy, appendectomy): the condition that leads to the procedure is the AE.
- Situations in which an untoward medical occurrence did not occur (social and/or convenience admission to a hospital).
- Anticipated day-to-day fluctuations of pre-existing disease(s) or condition(s) present or detected at the start of the study that do not worsen.

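### Urine dipstick is planned as a continuous measure (mean, SD, change from baseline); protein categories with unequal steps need counts and a shift table instead

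*Combined protocol and SAP*

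**What the plan says.** Urine dipstick is a named safety endpoint (Sections 3 and 9.4.2). The Section 9.1 summary table opens its list with "Continuous measures such as changes from baseline in laboratory test data, vital signs, 12-lead ECGs, cardiac function by echocardiography or MUGA scan, urine dipstick" and goes on to Lansky or KPS scores. Section 9.6.2 repeats the plan: "urine dipstick, and Lansky play scores or KPS scores will be summarized using descriptive statistics (mean, standard deviation, etc", at baseline, on treatment and as change from baseline. Neither section specifies counts by category, a shift table or a worst postbaseline value for dipstick.

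Adverse events have their own summary in Section 9.6.2: "The incidence of TEAEs and SAEs will be summarized by system organ class and preferred term".

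Elsewhere the protocol handles dipstick protein as a category. Section 5.1 requires a result below 2+, or further quantification, for entry. Under Section 6.6.3, a first result of 2+ or more "proteinuria on urine dipstick (or urinalysis) while on lenvatinib" calls for a protein-creatinine (P/C) test or a 24-hour collection, with details depending on age. A later rise in severity at the same dose level does the same. For participants aged 18 or over with 4+, "a 24-hour urinary protein result is required to confirm Grade 3 proteinuria". Grading does not use the dipstick code: "Grading according to CTCAE v5.0 will be based on the protein-creatinine ratio or 24-hour urinary protein result if available".

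**The concern.** A mean and SD presuppose that one unit means the same thing along the whole scale. Dipstick codes do not have that property. The results that matter are those crossing 2+ or reaching 4+, and a mean of codes reports neither.

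Proteinuria is an expected toxicity. Section 2.2.1.2 lists it among the treatment-emergent events seen in 40% or more of the earlier 31-patient osteosarcoma cohort. Under the Schedule of Activities, dipstick or urinalysis is also the only urine-protein measure scheduled for every participant; P/C ratio and 24-hour protein are obtained only when a result triggers them. At stake is whether the one routinely collected measure is reported in a form that a reader can use.

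**Working it through.** The plan gives no figure to reproduce. The check has two parts: the scale as the protocol defines it, and an illustration on assumed data.

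**1. Are the steps equal?** The inputs are the concentrations in Sections 6.6.3 and 8.3.6.2: 1+ is 10 mg/dL (or at least 10), 2+ is at least 100, and 4+ is at least 1000. No concentration is given for 3+. Using the stated lower bounds:

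- From 1+ to 2+ is one code step: 100 − 10 = 90 mg/dL, a factor of 10.
- From 2+ to 4+ is two code steps: 1000 − 100 = 900 mg/dL, or 900 / 2 = 450 mg/dL per step. The factor is 10 over two steps, or √10 ≈ 3.2 per step.

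The steps are unequal on the raw scale (90 against 450) and on the log scale (10 against about 3.2). A mean change in codes therefore corresponds to no fixed change in protein.

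**2. Can the mean separate different safety pictures?** Assumptions: negative = 0, 1+ = 1, 2+ = 2, 3+ = 3; every participant is negative at baseline; n is 36 (minimum planned enrolment, Section 1.1) or 150 (approximate upper estimate, same section). These are not trial data.

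- Mean change = (number moving × code reached) / n.
- SD is the usual sample SD with divisor n − 1.
- The 95% interval for x of n at 2+ or more is Clopper-Pearson: lower limit = 2.5% quantile of Beta(x, n − x + 1), or 0 if x = 0; upper limit = 97.5% quantile of Beta(x + 1, n − x).

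| n | Assumed change | Mean change | SD | Median | At 2+ or more (95% CI) |
|---|---|---|---|---|---|
| 36 | 4 go to 3+ | 4 × 3 / 36 = 0.33 | 0.96 | 0 | 4/36 = 11.1% (3.1 to 26.1) |
| 36 | 12 go to 1+ | 12 × 1 / 36 = 0.33 | 0.48 | 0 | 0/36 = 0% (0 to 9.7) |
| 150 | 15 go to 3+ | 15 × 3 / 150 = 0.30 | 0.90 | 0 | 15/150 = 10.0% (5.7 to 16.0) |
| 150 | 45 go to 1+ | 45 × 1 / 150 = 0.30 | 0.46 | 0 | 0/150 = 0% (0 to 2.4) |

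Within each n the mean and the median agree exactly, although one group has participants past the protocol's own trigger and the other has none. Only the SD differs. A table of categories separates the two at once.

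**The case against.** The strongest reply is that proteinuria reaches the report by another route. Treatment-emergent events are tabulated by preferred term. A 2+ result on treatment triggers quantification, and grading then rests on the P/C ratio or 24-hour protein. Clinically significant urinalysis findings count as adverse events (Section 10.3.2: "Any abnormal laboratory test results (hematology, clinical chemistry, or urinalysis) or other safety assessments"), and the note to Table 3 says "Collect all CTC grades of adverse events, decreasing and increasing grade". The 40% figure from the earlier cohort is itself an adverse-event frequency. All of this stands. A reader might infer that the planned summary hides the proteinuria signal; the documents do not support that.

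The adverse-event route does not replace a proper dipstick summary, however. Section 9.6.2 plans incidence by preferred term and does not mention CTCAE grade. An abnormal urinalysis becomes an event only if the investigator judges it clinically significant.

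A second reply is that the SD is reported and that the trailing et cetera leaves other statistics open. The SD in the illustration does differ (0.96 against 0.48), which hints at a skewed minority. It does not tell the reader how many participants reached 2+ or 4+, and an open-ended list prespecifies nothing.

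On performance scores, a reader might infer that Lansky and KPS are averaged together, or that a mean of them is invalid. The text joins the two scales with the word or, and its pooling statement concerns indications, so separate summaries fit the wording. Both scales run from 0 to 100 in steps of 10, and a descriptive mean with no test attached is acceptable. What remains is a gap in wording: nothing says that the scales are kept apart, or how change from baseline is taken if a participant crosses the age boundary during treatment estimated at one year.

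**Conclusion.** The point holds for urine dipstick and is minor. Treating dipstick protein as continuous conflicts with the protocol's own concentrations and with the way it uses the result. On assumed data at n = 36, the same mean change of 0.33 is compatible with 11.1% or 0% of participants at 2+ or more; at n = 150, a mean change of 0.30 is compatible with 10.0% or 0%. Those sizes depend on the assumed coding and scenarios. The conclusion about unequal steps depends only on the stated concentrations.

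Proteinuria adverse events are reported separately, so the weakness is confined to the dipstick endpoint. These are descriptive safety summaries: the primary endpoint and its analysis are untouched.

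For Lansky and KPS only a clarification is needed. The age boundary is inconsistent: Lansky applies up to and including 16 years in the Schedule of Activities and Sections 5.1 and 8.3.6.4, but under 16 years in Appendix 9. As written, a 16-year-old could be scored on either scale.

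**What to change.** In both Section 9.1 and Section 9.6.2, so that the two stay consistent:

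- Remove urine dipstick from the continuous measures.
- For dipstick protein, report number and percentage by category, a shift table from baseline to worst postbaseline category, and the proportions reaching 2+ or more and 4+.
- State that Lansky and KPS are summarised separately, with change from baseline taken only within the same scale.

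Separately, reconcile the Lansky age boundary between Appendix 9 and the other sections.

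The cost is one or two standard table shells. The dipstick results are already collected, so no new data are needed. If no amendment is due, the opening of Section 9 allows changes to non-confirmatory analyses to be documented in the supplemental SAP.

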9.6.3 Summary of Baseline Characteristics, Demographics, and Other Analyses

Baseline characteristics will be assessed by the use of tables and/or graphs for each tumor type with at least 9 evaluable participants enrolled. No statistical hypothesis tests will be performed on these characteristics. The number and percentage of participants screened, allocated, the primary reasons for screening failure, and the primary reason for discontinuation will be displayed. Demographic variables (eg, age, gender), baseline characteristics, and prior and concomitant medications, medical/surgical history will be summarized by descriptive statistics or categorical tables.

9.6.4 Statistical Methods for Pharmacokinetic, Pharmacodynamic, and Other Biomarker Analyses

Plasma concentrations of lenvatinib versus time data will be tabulated with descriptive statistics and the individual data graphed. Plasma concentrations of lenvatinib versus time data will be analyzed using a population PK approach to estimate population PK parameters. The analysis will be detailed in an analysis plan at a later date.

Pharmacokinetic data will be summarized using n, mean, standard deviation, percent coefficient of variation, geometric mean, median, minimum, and maximum.

9.7 Interim Analyses

9.7.1 Safety Interim Analyses

[figure not shown]
The DMC will review accumulating safety data periodically to provide an opportunity to terminate the study early if there are safety concerns. The timing of the safety monitoring will be specified in the DMC charter.

9.7.2 Efficacy Interim Analysis

CCI

CCI

CCI

9.8 Multiplicity

No multiplicity adjustment is required because each disease indication will be evaluated independently.

9.9 Sample Size and Power Calculations

CCI

CCI

9.10 Subgroup Analyses

No subgroup analysis is planned.

9.11 Compliance (Medication Adherence)

Drug accountability data for study treatment will be collected during the study. Any deviation from protocol-directed administration will be reported.

9.12 Extent of Exposure

Extent of exposure for a participant will be measured by number of cycles and number of days in which the participant receives the study medication. Summary statistics will be provided on extent of exposure for the safety analysis population.

10 SUPPORTING DOCUMENTATION AND OPERATIONAL CONSIDERATIONS

10.1 Appendix 1: Regulatory, Ethical, and Study Oversight Considerations

10.1.1 Code of Conduct for Clinical Trials

Merck Sharp & Dohme LLC, Rahway, NJ, USA (MSD)

Code of Conduct for Interventional Clinical Trials

I. Introduction

A. Purpose

MSD, through its subsidiaries, conducts clinical trials worldwide to evaluate the safety and effectiveness of our products. As such, we are committed to designing, implementing, conducting, analyzing, and reporting these trials in compliance with the highest ethical and scientific standards. Protection of participants in clinical trials is the overriding concern in the design and conduct of clinical trials. In all cases, MSD clinical trials will be conducted in compliance with local and/or national regulations (including all applicable data protection regulations), and International Council for Harmonisation Good Clinical Practice (ICH GCP), and also in accordance with the ethical principles that have their origin in the Declaration of Helsinki.

B. Scope

Highest ethical and scientific standards shall be endorsed for all clinical interventional investigations sponsored by MSD irrespective of the party (parties) employed for their execution (e.g., contract research organizations, collaborative research efforts). This Code is not intended to apply to trials that are observational in nature, or which are retrospective. Further, this Code does not apply to investigator initiated trials, which are not under the full control of MSD.

II. Scientific Issues

A. Trial Conduct

1. Trial Design

Except for pilot or estimation trials, clinical trial protocols will be hypothesis driven to assess safety, efficacy and/or pharmacokinetic or pharmacodynamic indices of MSD or comparator products. Alternatively, MSD may conduct outcomes research trials, trials to assess or validate various endpoint measures, or trials to determine patient preferences, etc.

The design (i.e., participant population, duration, statistical power) must be adequate to address the specific purpose of the trial. Participants must meet protocol entry criteria to be enrolled in the trial.

2. Site Selection

MSD selects investigative sites based on medical expertise, access to appropriate participants, adequacy of facilities and staff, previous performance in clinical trials, as well as budgetary considerations. Prior to trial initiation, sites are evaluated by MSD personnel (or individuals acting on behalf of MSD) to assess the ability to successfully conduct the trial.

3. Site Monitoring/Scientific Integrity

Investigative trial sites are monitored to assess compliance with the trial protocol and Good Clinical Practice (GCP). MSD reviews clinical data for accuracy, completeness, and consistency. Data are verified versus source documentation according to standard operating procedures. Per MSD policies and procedures, if fraud,

scientific/research misconduct or serious GCP non compliance is suspected, the issues are investigated. When necessary, the clinical site will be closed, the responsible regulatory authorities and ethics review committees notified.

B. Publication and Authorship

Regardless of trial outcome, MSD commits to publish the primary and secondary results of its registered trials of marketed products in which treatment is assigned, according to the pre specified plans for data analysis. To the extent scientifically appropriate, MSD seeks to publish the results of other analyses it conducts that are important to patients, physicians, and payers. Some early phase or pilot trials are intended to be hypothesis generating rather than hypothesis testing; in such cases, publication of results may not be appropriate since the trial may be underpowered and the analyses complicated by statistical issues such as multiplicity.

MSD's policy on authorship is consistent with the recommendations published by the International Committee of Medical Journal Editors (ICMJE). In summary, authorship should reflect significant contribution to the design and conduct of the trial, performance or interpretation of the analysis, and/or writing of the manuscript. All named authors must be able to defend the trial results and conclusions. MSD funding of a trial will be acknowledged in publications.

III. Participant Protection

A. Regulatory Authority and Ethics Committee Review (Institutional Review Board [IRB]/Independent Ethics Committee [IEC])

All protocols and protocol amendments will be submitted by MSD for regulatory authority acceptance/authorization prior to implementation of the trial or amendment, in compliance with local and/or national regulations.

The protocol, protocol amendment(s), informed consent form, investigator's brochure, and other relevant trial documents must be reviewed and approved by an IRB/IEC before being implemented at each site, in compliance with local and/or national regulations. Changes to the protocol that are required urgently to eliminate an immediate hazard and to protect participant safety may be enacted in anticipation of ethics committee approval. MSD will inform regulatory authorities of such new measures to protect participant safety, in compliance with local and/or national regulations.

B. Safety

The guiding principle in decision making in clinical trials is that participant welfare is of primary importance. Potential participants will be informed of the risks and benefits of, as well as alternatives to, trial participation. At a minimum, trial designs will take into account the local standard of care.

All participation in MSD clinical trials is voluntary. Participants enter the trial only after informed consent is obtained. Participants may withdraw from an MSD trial at any time, without any influence on their access to, or receipt of, medical care that may otherwise be available to them.

C. Confidentiality

MSD is committed to safeguarding participant confidentiality, to the greatest extent possible. Unless required by law, only the investigator, Sponsor (or individuals acting on behalf of MSD), ethics committee, and/or regulatory authorities will have access to confidential medical records that might identify the participant by name.

D. Genomic Research

Genomic research will only be conducted in accordance with a protocol and informed consent authorized by an ethics committee.

IV. Financial Considerations

A. Payments to Investigators

Clinical trials are time and labor intensive. It is MSD's policy to compensate investigators (or the sponsoring institution) in a fair manner for the work performed in support of MSD trials. MSD does not pay incentives to enroll participants in its trials. However, when enrollment is particularly challenging, additional payments may be made to compensate for the time spent in extra recruiting efforts.

MSD does not pay for participant referrals. However, MSD may compensate referring physicians for time spent on chart review and medical evaluation to identify potentially eligible participants.

B. Clinical Research Funding

Informed consent forms will disclose that the trial is sponsored by MSD, and that the investigator or sponsoring institution is being paid or provided a grant for performing the trial. However, the local ethics committee may wish to alter the wording of the disclosure statement to be consistent with financial practices at that institution. As noted above, all publications resulting from MSD trials will indicate MSD as a source of funding.

C. Funding for Travel and Other Requests

Funding of travel by investigators and support staff (e.g., to scientific meetings, investigator meetings, etc.) will be consistent with local guidelines and practices.

V. Investigator Commitment

Investigators will be expected to review MSD's Code of Conduct as an appendix to the trial protocol, and in signing the protocol, agree to support these ethical and scientific standards.

